8.10 Subgroup Analyses and Effect of Baseline Factors

To determine whether the treatment effect is consistent across various subgroups, the estimate of the between-group treatment effect (with a nominal 95% CI) for the primary endpoint will be estimated and plotted within each category of the following classification variables:

- Stratification factors
 - Disease status (refractory vs. sensitive to lenalidomide).
 - Number of prior therapies (2 vs. three or more)
- Sex (female vs. male)
- ECOG status (0 vs. 1)
- Geographic region
- Race (White vs. Non White)
- Age (< 75 vs. ≥ 75 years)

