8.9 Sample Size and Power Calculations

The study will randomize approximately 300 subjects in a 1:1 ratio among the two treatment arms: pembrolizumab in combination with SOC (combination therapy), and SOC (control).

With ~ 210 subjects at IA1, the study has ~ 88.7% power for detecting a 25% difference in ORR (55% vs. 30%) at 0.5% level of significance (one-sided).

IA2, the final PFS analysis of the study will be performed after approximately 236 PFS events have been observed, and this will occur ~20 months after the first subject is enrolled.

The final OS analysis of the study will be performed 10 months after the PFS analysis or after 182 deaths have been observed in the trial, whichever comes first.

For the primary endpoint PFS, the study has ~90.6% power to detect a hazard ratio of 0.635 (pembrolizumab in combination with SOC vs. SOC) at alpha = 1.5% (one-sided). The sample size calculation is based on the following assumptions: 1) progression-free survival follows an exponential distribution with a median of 4 months in the control arm (Arm B), 2) an enrollment period of 14 months and at least 6 months follow-up, 3) a yearly dropout rate of 5% and 4) ORR is negative.

For the primary endpoint OS, the study has ~80.5% power to detect a hazard ratio of 0.600 (pembrolizumab in combination with SOC vs. SOC) at alpha = 0.5% (one-sided). These calculations are based on the following assumptions: 1) OS follows an exponential distribution with a median of 12.7 months in the control arm (Arm B), 2) an enrollment period of 14 months and at least 16 months follow-up, 3) a yearly dropout rate of 2% and 4) PFS is negative.

The assumed median PFS and OS in the control arm (Arm B) are observed for standard of care in treatment of refractory or relapsed multiple myeloma [46]

The sample size and power calculations were performed in the software EAST 6.

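### Section 8.10 sets out to judge whether the treatment effect is consistent across subgroups, but plans only within-category estimates and no between-level contrast or its precision

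*Combined protocol and SAP*

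**What the plan says.** Section 8.10 gives the purpose and the method in one sentence. It reads "To determine whether the treatment effect is consistent across various subgroups, the estimate of the between-group treatment effect (with a nominal 95% CI"), and continues "for the primary endpoint will be estimated and plotted within each category of the following classification variables". Seven factors follow: the two stratification factors (lenalidomide status and number of prior therapies), sex, ECOG status, geographic region, race and age. Six are two-level, for example "Age (< 75 vs. ≥ 75 years"). The categories of region are not listed.

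No treatment-by-subgroup term, heterogeneity statistic or criterion for consistency appears in Section 8.10 or elsewhere in Section 8. The Cox models for PFS, OS and PFS2 in Section 8.6.1 each carry treatment as the only covariate. The supplemental SAP is cited for other items, but Section 8.10 does not refer subgroup consistency to it. Section 8.10 speaks of one primary endpoint, whereas Section 8.1 names two, PFS and OS.

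The design figures used below are in Section 8.9: "IA2, the final PFS analysis of the study will be performed after approximately 236 PFS events have been observed"; "For the primary endpoint PFS, the study has ~90.6% power to detect a hazard ratio of 0.635 (pembrolizumab in combination with SOC vs. SOC") at one-sided 1.5%; the final OS analysis 10 months after the PFS analysis or "after 182 deaths have been observed in the trial, whichever comes first"; and "For the primary endpoint OS, the study has ~80.5% power to detect a hazard ratio of 0.600 (pembrolizumab in combination with SOC vs. SOC") at one-sided 0.5%.

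**The concern.** The question asked is whether the hazard ratio is the same in both levels of a factor. The planned interval describes the hazard ratio within one level, and its natural reference value on a forest plot is 1. Whether it includes 1 depends heavily on how many events the level holds. A small level can therefore look as if it has no effect when its effect is identical to that of everyone else.

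The quantity that answers the question is the ratio of the two hazard ratios. Its width also limits how firmly anyone may claim consistency, and the planned display does not show it. This matters most for the two stratification factors of Section 5.4, which the sponsor itself chose as important. No confirmatory test, alpha allocation or sample size is affected.

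**Working it through.** **Inputs.** Section 8.9 gives 236 PFS events with hazard ratio 0.635, 182 deaths with hazard ratio 0.600, and 1:1 allocation. Subgroup shares and the number of regions are not given, so they are assumed and varied.

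**Reproducing the plan's power.** With D events and 1:1 allocation, the SE of the log hazard ratio is about 2/√D, and power is Φ(|ln HR|·√D/2 − z).
- PFS: 0.4541 × √236/2 = 3.488; less 2.170 gives 1.318; Φ = 90.6%. The plan states about 90.6%.
- OS: 0.5108 × √182/2 = 3.446; less 2.576 gives 0.870; Φ = 80.8%, or 80.4% at the final-look level of 0.0048. The plan states about 80.5%.

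**One category under a fully consistent effect.** A category with share p of the events has SE = 2/√(pD). The chance that its 95% interval includes 1 is 1 − Φ(|ln HR|/SE − 1.96). For PFS with p = 0.20: 47.2 events, SE 0.291, 0.4541/0.291 = 1.560, and 1 − Φ(−0.400) = 66%.

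| Share of events | PFS (236 events, HR 0.635) | OS (182 events, HR 0.600) |
|---|---|---|
| 10% | 80% | 81% |
| 20% | 66% | 66% |
| 30% | 52% | 53% |
| 40% | 40% | 41% |
| 50% | 31% | 32% |

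**All factors together.** Trials were simulated with one common hazard ratio. The log hazard ratio from d events was taken as Normal(ln HR, 4/d), and the same events were re-split by each factor, with factors independent. PFS results:

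| Assumed splits | At least one category interval includes 1 | At least one unadjusted 5% contrast |
|---|---|---|
| Six factors 50/50, region left out | 81% | 27% |
| Seven two-level factors, all 50/50 | 82% | 30% |
| Five 50/50, age with 15-30% in the smaller level, no region | 84-90% | 26-27% |
| Five 50/50, three equal regions, age 25% | 93% | 31% |
| Six 60/40, three regions | 94% | 30% |
| Seven two-level, smaller shares 20, 50, 40, 40, 40, 20, 20% | 96% | 30% |
| Smaller shares 15-45%, three regions | 98% | 30% |

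The OS figures are close: 82% with six 50/50 factors and 98% with uneven splits and three regions. The last column agrees with simple arithmetic for independent contrasts: 1 − 0.95⁶ = 26% and 1 − 0.95⁷ = 30%. Each contrast taken singly errs in 5%.

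**Sensitivity to the true effect.** With 236 events and a true hazard ratio of 0.5, the middle column falls to 24% (seven factors 50/50), 70% (the 20, 50, 40, 40, 40, 20, 20% set) and 78% (uneven with three regions).

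**Precision of the contrast.** For a 20/80 split of 236 events, the SE of the log ratio of hazard ratios is √(4/47.2 + 4/188.8) = 0.325. Since exp(1.96 × 0.325) = 1.9, the ratio is known to within a factor of about 1.9 either way. For a 50/50 split the SE is 0.260 and the factor is 1.7. For 80% power at two-sided 5%, the true ratio would have to be about exp(−2.80 × 0.325) = 0.40 (20/80) or exp(−2.80 × 0.260) = 0.48 (50/50).

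**The case against.** The strongest reply is that Section 8.10 is descriptive and never adopts 'the interval includes 1' as its test of consistency. A reader may infer that rule, but it is not in the text. Point estimates are plotted too and can be compared with each other and with the overall estimate. The intervals are labelled nominal, and Section 8.6.1 asks for caution with results outside the error-control strategy. This stands: the percentages above measure how misleading a natural misreading would be, not an error rate of a planned procedure.

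A reader might also infer that a real difference would go unestimated. That goes too far. The two levels of a factor contain different subjects, so the ratio and its SE can be approximated from the planned hazard ratios and intervals, as was done above. What is missing is the stated contrast, its width and a rule for reading it.

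Contrasts also give false signals. The 80-98% range is a statement about all factors, so its fair comparator is about 25-31% for at least one contrast, not 5%. The contrasts have low power and would rarely settle the matter.

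Finally, Section 8.0 records that treatment was closed after the clinical hold and that the analysis may be modified and reported in the CSR. The practical stake is smaller than in the trial as designed. If fewer events accrue, however, category intervals widen further and their relation to 1 tells even less.

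**Conclusion.** The point holds as a mismatch between aim and method. Section 8.10 promises to determine consistency and supplies no between-level contrast, no statement of its precision and no rule for judging it. The single-category figures (66% at 20% of events, 31% at 50%) rest only on the plan's PFS design values and the usual normal approximation. The joint figure of about 80-98% also rests on assumed splits, independent factors and a true hazard ratio near the design value. 'Usually' is therefore justified. 'Almost always' might be inferred from the upper end, but the documents give no subgroup shares to support it, and the figure drops to 24-78% at a true hazard ratio of 0.5. This is a low-cost improvement to an exploratory analysis and casts no doubt on the primary tests.

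**What to change.** In Section 8.10, for both PFS and OS:
- Add, for each factor, the ratio of hazard ratios between levels with a nominal 95% interval, from a Cox model with treatment, factor and treatment-by-factor terms. Keep the randomisation stratification where the factor is not itself a stratifier.
- For a factor with more than two levels, as region may be, give contrasts against a named reference level or a global heterogeneity test.
- Show the number of events per level on the forest plot.
- Label the contrasts exploratory and unadjusted.
- State that consistency is judged from the ratio and its width, that a category interval including 1 is not evidence of inconsistency, and that a non-significant contrast does not show consistency.

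The cost is one model per factor and endpoint and one more column on each forest plot. The drawback is a few more unadjusted, low-power descriptive intervals.

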8.11 COMPLIANCE (MEDICATION ADHERENCE)

Drug accountability data for trial treatment will be collected during the study. Any deviation from protocol-directed administration will be reported.

8.12 EXTENT OF EXPOSURE

The extent of exposure will be summarized as duration of treatment in cycles.

9.0 LABELING, PACKAGING, STORAGE AND RETURN OF CLINICAL SUPPLIES

9.1 Investigational Product

The investigator shall take responsibility for and shall take all steps to maintain appropriate records and ensure appropriate supply, storage, handling, distribution and usage of investigational product in accordance with the protocol and any applicable laws and regulations.

Clinical Supplies will be provided by the Sponsor as summarized in [Table 18](#).

Clinical supplies will be packaged to support enrollment and replacement subjects as required. When a replacement subject is required, the Sponsor or designee needs to be contacted prior to dosing the replacement supplies.

Table 18 Product Descriptions

Product Name & Potency	Dosage Form	Source/Additional Information
MK-3475 100 mg/4 mL	Solution for Injection	Provided centrally by the Sponsor.
Pomalidomide	Hard capsule	Provided centrally by the Sponsor except in specific countries where commercial product may be sourced locally.
Dexamethasone	Tablet	Provided centrally by the Sponsor except in specific countries where commercial product may be sourced locally.

All other supplies not indicated in [Table 18](#) above will be provided centrally by the Sponsor or locally by the trial site, subsidiary or designee, depending on local country operational or regulatory requirements.

For any commercially available product that is provided by the trial site, subsidiary or designee every attempt will be made to source these supplies from a single lot/batch number.

The trial site is responsible to record the lot number, manufacturer and expiry date for any locally purchased product as per local guidelines unless otherwise instructed by the Sponsor.

9.2 Packaging and Labeling Information

Clinical supplies will be affixed with a clinical label in accordance with regulatory requirements.

Subjects will receive open label vials as required to support treatment. No kitting is required.

9.3 Clinical Supplies Disclosure

This trial is open-label; therefore, the subject, the trial site personnel, the Sponsor and/or designee are not blinded. Treatment (name, strength or potency) is included in the label text; random code/disclosure envelopes or lists are not provided.

9.4 Storage and Handling Requirements

Clinical supplies must be stored in a secure, limited-access location under the storage conditions specified on the label.

Receipt and dispensing of trial medication must be recorded by an authorized person at the trial site.

Clinical supplies may not be used for any purpose other than that stated in the protocol.

9.5 Discard/Destruction/Returns and Reconciliation

The investigator is responsible for keeping accurate records of the clinical supplies received from the Sponsor or designee, the amount dispensed to and returned by the subjects and the amount remaining at the conclusion of the trial. For all trial sites, the local country Sponsor personnel or designee will provide appropriate documentation that must be completed for drug accountability and return, or local discard and destruction if appropriate. Where local discard and destruction is appropriate, the investigator is responsible for ensuring that a local discard/destruction procedure is documented.

9.6 Standard Policies

Trial site personnel will have access to a central electronic treatment allocation/randomization system (IVRS/IWRS system) to allocate subjects, to assign treatment to subjects and to manage the distribution of clinical supplies. Each person accessing the IVRS system must be assigned an individual unique PIN. They must use only their assigned PIN to access the system, and they must not share their assigned PIN with anyone.

10.0 ADMINISTRATIVE AND REGULATORY DETAILS

10.1 Confidentiality

10.1.1 Confidentiality of Data

By signing this protocol, the investigator affirms to the Sponsor that information furnished to the investigator by the Sponsor will be maintained in confidence, and such information will be divulged to the institutional review board, ethics review committee (IRB/ERC) or similar or expert committee; affiliated institution and employees, only under an appropriate understanding of confidentiality with such board or committee, affiliated institution and employees. Data generated by this trial will be considered confidential by the investigator, except to the extent that it is included in a publication as provided in the Publications section of this protocol.

10.1.2 Confidentiality of Subject Records

By signing this protocol, the investigator agrees that the Sponsor (or Sponsor representative), IRB/ERC, or regulatory authority representatives may consult and/or copy trial documents in order to verify worksheet/case report form data. By signing the consent form, the subject agrees to this process. If trial documents will be photocopied during the process of verifying worksheet/case report form information, the subject will be identified by unique code only; full names/initials will be masked prior to transmission to the Sponsor.

By signing this protocol, the investigator agrees to treat all subject data used and disclosed in connection with this trial in accordance with all applicable privacy laws, rules and regulations.

10.1.3 Confidentiality of Investigator Information

By signing this protocol, the investigator recognizes that certain personal identifying information with respect to the investigator, and all subinvestigators and trial site personnel, may be used and disclosed for trial management purposes, as part of a regulatory submissions, and as required by law. This information may include:

1. name, address, telephone number and e-mail address;
2. hospital or clinic address and telephone number;
3. curriculum vitae or other summary of qualifications and credentials; and
4. other professional documentation.

Consistent with the purposes described above, this information may be transmitted to the Sponsor, and subsidiaries, affiliates and agents of the Sponsor, in your country and other countries, including countries that do not have laws protecting such information. Additionally, the investigator's name and business contact information may be included when reporting certain serious adverse events to regulatory authorities or to other investigators. By signing this protocol, the investigator expressly consents to these uses and disclosures.

If this is a multicenter trial, in order to facilitate contact between investigators, the Sponsor may share an investigator's name and contact information with other participating investigators upon request.

10.1.4 Confidentiality of IRB/IEC Information

The Sponsor is required to record the name and address of each IRB/IEC member that reviews and approves this trial. The Sponsor is also required to document that each IRB/IEC meets regulatory and ICH GCP requirements by requesting and maintaining records of the names and qualifications of the IRB/IEC members and to make these records available for regulatory agency review upon request by those agencies.

10.2 Compliance with Financial Disclosure Requirements

Financial Disclosure requirements are outlined in the US Food and Drug Administration Regulations, Financial Disclosure by Clinical Investigators (21 CFR Part 54). It is the Sponsor's responsibility to determine, based on these regulations, whether a request for Financial Disclosure information is required. It is the investigator's/subinvestigator's responsibility to comply with any such request.

The investigator/subinvestigator(s) agree, if requested by the Sponsor in accordance with 21 CFR Part 54, to provide his/her financial interests in and/or arrangements with the Sponsor to allow for the submission of complete and accurate certification and disclosure statements. The investigator/subinvestigator(s) further agree to provide this information on a Certification/Disclosure Form, commonly known as a financial disclosure form, provided by the Sponsor. The investigator/subinvestigator(s) also consent to the transmission of this information to the Sponsor in the United States for these purposes. This may involve the transmission of information to countries that do not have laws protecting personal data.

10.3 Compliance with Law, Audit and Debarment

By signing this protocol, the investigator agrees to conduct the trial in an efficient and diligent manner and in conformance with this protocol; generally accepted standards of Good Clinical Practice (e.g., International Conference on Harmonization of Technical Requirements for Registration of Pharmaceuticals for Human Use Good Clinical Practice: Consolidated Guideline and other generally accepted standards of good clinical practice); and all applicable federal, state and local laws, rules and regulations relating to the conduct of the clinical trial.

The Code of Conduct, a collection of goals and considerations that govern the ethical and scientific conduct of clinical investigations sponsored by Merck, is provided in Section 12.1 - Merck Code of Conduct for Clinical Trials.

The investigator also agrees to allow monitoring, audits, IRB/ERC review and regulatory authority inspection of trial-related documents and procedures and provide for direct access to all trial-related source data and documents.

The investigator agrees not to seek reimbursement from subjects, their insurance providers or from government programs for procedures included as part of the trial reimbursed to the investigator by the Sponsor.

The investigator shall prepare and maintain complete and accurate trial documentation in compliance with Good Clinical Practice standards and applicable federal, state and local laws, rules and regulations; and, for each subject participating in the trial, provide all data, and, upon completion or termination of the clinical trial, submit any other reports to the Sponsor as required by this protocol or as otherwise required pursuant to any agreement with the Sponsor.

Trial documentation will be promptly and fully disclosed to the Sponsor by the investigator upon request and also shall be made available at the trial site upon request for inspection, copying, review and audit at reasonable times by representatives of the Sponsor or any regulatory authorities. The investigator agrees to promptly take any reasonable steps that are requested by the Sponsor as a result of an audit to cure deficiencies in the trial documentation and worksheets/case report forms.

The investigator must maintain copies of all documentation and records relating to the conduct of the trial in compliance with all applicable legal and regulatory requirements. This documentation includes, but is not limited to, the protocol, worksheets/case report forms, advertising for subject participation, adverse event reports, subject source data, correspondence with regulatory authorities and IRBs/ERCs, consent forms, investigator's curricula vitae, monitor visit logs, laboratory reference ranges, laboratory certification or quality control procedures and laboratory director curriculum vitae. By signing this protocol, the investigator agrees that documentation shall be retained until at least 2 years after the last approval of a marketing application in an ICH region or until there are no pending or contemplated marketing applications in an ICH region or until at least 2 years have elapsed since the formal discontinuation of clinical development of the investigational product. Because the clinical development and marketing application process is variable, it is anticipated that the retention period can be up to 15 years or longer after protocol database lock. The Sponsor will determine the minimum retention period and notify the investigator

when documents may be destroyed. The Sponsor will determine the minimum retention period and upon request, will provide guidance to the investigator when documents no longer need to be retained. The sponsor also recognizes that documents may need to be retained for a longer period if required by local regulatory requirements. All trial documents shall be made available if required by relevant regulatory authorities. The investigator must consult with and obtain written approval by the Sponsor prior to destroying trial and/or subject files.

ICH Good Clinical Practice guidelines recommend that the investigator inform the subject's primary physician about the subject's participation in the trial if the subject has a primary physician and if the subject agrees to the primary physician being informed.

The investigator will promptly inform the Sponsor of any regulatory authority inspection conducted for this trial.

Persons debarred from conducting or working on clinical trials by any court or regulatory authority will not be allowed to conduct or work on this Sponsor's trials. The investigator will immediately disclose in writing to the Sponsor if any person who is involved in conducting the trial is debarred or if any proceeding for debarment is pending or, to the best of the investigator's knowledge, threatened.

In the event the Sponsor prematurely terminates a particular trial site, the Sponsor will promptly notify that trial site's IRB/IEC.

According to European legislation, a Sponsor must designate an overall coordinating investigator for a multi-center trial (including multinational). When more than one trial site is open in an EU country, Merck, as the Sponsor, will designate, per country, a national principal coordinator (Protocol CI), responsible for coordinating the work of the principal investigators at the different trial sites in that Member State, according to national regulations. For a single-center trial, the Protocol CI is the principal investigator. In addition, the Sponsor must designate a principal or coordinating investigator to review the trial report that summarizes the trial results and confirm that, to the best of his/her knowledge, the report accurately describes the conduct and results of the trial [Clinical Study Report (CSR) CI]. The Sponsor may consider one or more factors in the selection of the individual to serve as the Protocol CI and or CSR CI (e.g., availability of the CI during the anticipated review process, thorough understanding of clinical trial methods, appropriate enrollment of subject cohort, timely achievement of trial milestones). The Protocol CI must be a participating trial investigator.

